#### 6.1.1. Participant Disposition

A summary of the number and percentage of participants who completed the study as well as those who prematurely withdrew from the study will be provided. Reasons for study withdrawal will be summarised. For those who have neither completed nor withdrawn, they will be categorized as on study intervention or in follow up.

A summary of study intervention status will be provided. This display will show the number and percentage of participants who have completed the scheduled study intervention, are ongoing with study intervention, or have discontinued study intervention prematurely, as well as primary reasons for discontinuation of study intervention.

#### 6.1.2. Demographic and Baseline Characteristics

The demographic characteristics including age, gender, ethnicity, height/weight at screening and race will be summarised with descriptive statistics. In addition, the following age categories will be summarised: 12-17, 18-64 and  $\geq 65$  based on the Enrolled Analysis Set.

History of tobacco use will be summarised (i.e., Never, Current, Former).

A summary of baseline cardiovascular family history assessment will be presented. The number of participants who report a family history of cardiovascular risk factors will be summarised.

Past medical conditions and current medical conditions as of Baseline will be summarised respectively. Past medical conditions are those conditions which were considered no longer present at each participant's baseline visit. Current medical conditions are those conditions which were considered present/ongoing at each participant's baseline visit.

Lung function, pre bronchodilator FEV1, FVC, percent predicted FEV1, and FEV1/FVC at baseline visit 1 will be summarised.

The following data will be summarized using baseline data from previous study 206713 or 213744 where ICS dose at baseline refers to baseline in previous study:

- Summary of Asthma History and Baseline Disease Characteristics

- Summary of Asthma Exacerbation History

### **6.1.3. Protocol Deviations**

Important protocol deviations will be summarised.

Protocol deviations will be tracked by the study team throughout the conduct of the study. These protocol deviations will be reviewed to identify those considered as important as follows:

- Data will be reviewed prior to freezing the database to ensure all important deviations are captured and categorised in the protocol deviations dataset.
- This dataset will be the basis for the summaries of important protocol deviations.

### **6.1.4. Concomitant Medications**

Concomitant medications will be coded using both the GSK Drug and WHO Drug dictionaries. However, the summary will be based on GSK Drug dictionary only. The summary of concomitant medications will show the number and percentage of participants taking concomitant medications by Ingredient. Multi-ingredient products will be summarised by their separate ingredients rather than as a combination of ingredients. Summaries will be split into asthma and non-asthma concomitant medications. Summaries for asthma medication will be categorised by Respiratory Medication Class (RMC) dictionary. Anatomical Therapeutic Chemical (ATC) classifications will appear in the summary for non-asthma medication.

The summary of concomitant medications will include:

- Summary of Asthma Concomitant Medications Taken During Treatment by Respiratory Medication Class Group
- Summary of Exacerbation Concomitant Medications Taken for an Exacerbation During Treatment by Respiratory Medication Class Group
- Summary of Non-Asthma Concomitant Medications Taken During Treatment

Note: 'during treatment' refers to on treatment period in this study (212895).

## **6.2. Appendix 2 Data Derivations Rule**

### **6.2.1. Criteria for Potential Clinical Importance**

Reference ranges for all laboratory parameters collected throughout the study are provided by the laboratory. A laboratory value that is outside the reference range is considered either high abnormal (value above the upper limit of the reference range) or low abnormal (value below the lower limit of the reference range). Note: a high abnormal or low abnormal laboratory value is not necessarily of clinical concern.

The following criteria will be used to flag potential clinical importance:

**Laboratory Values**

Haematology				
Laboratory Parameter	Units	Category	Clinical Concern Range	
			Low Flag (< x)	High Flag (>x)
CCI				

Clinical Chemistry				
Laboratory Parameter	Units	Category	Clinical Concern Range	
			Low Flag (< x)	High Flag (>x)
Calcium	mmol/L	3+ years	1.50	3.24
Creatinine	Umol/L	12+ years		>5 x ULN
Glucose	mmol/L	1+ years	2.2	27.8
Potassium	mEq/L	3+ years	2.8	6.5
Magnesium	mmol/L	6+years	0.3	2.5
Phosphorus	mmol/L	3+years	0.32	
Sodium	mEq/L	0+ years	120	160
ALT	U/L	12+ years		>239
Creatine Phosphokinase	IU/L	12+years		>5xULN

Liver Function				
Laboratory Parameter	Units	Category	Clinical Concern Range	
			High Flag (>x)	
ALT/SGPT	U/L	High	3 x ULN	
AST/SGOT	U/L	High	3 x ULN	
AlkPhos	U/L	High	3 x ULN	
T Bilirubin	µmol/L	High	34.2	
ALT, Bilirubin	U/L		ALT $\geq$ 3xULN and Bilirubin $\geq$ 2xULN (>35% direct)	
ALT, INR			ALT $\geq$ 3xULN and INR > 1.5	

**6.2.2. Study Phases**

Assessments and events will be classified according to the time of occurrence relative to the study intervention period.

### 6.2.2.1. Study Phases in General (unless specified in Section 6.2.2.2 to Section 6.2.2.3)

Assessments and events will be classified according to the time of occurrence relative to study treatment start date.

Study Phase	Definition
Pre-Treatment	Assessment/Event Date $\leq$ Study Treatment Start Date
On-Treatment	Study Treatment Start Date $<$ Assessment/Event Date $\leq$ Date of Last Dose of Study Treatment + 182 days
Post-Treatment	Assessment/Event Date $>$ Date of Last Dose of Study Treatment + 182 days

### 6.2.2.2. Study Phases for Concomitant Medication

Study Phase	Definition
Pre-Treatment	Concomitant medication (CM) start date $<$ Study Treatment start date
On-Treatment	If CM start date $<$ Study Treatment start date and CM stop date $\geq$ Study Treatment start date or If Study Treatment start date $<$ CM start Date $<$ Last Dose of Study Treatment date + 182 days
Post-Treatment	If CM start date $<$ Last Dose of Study Treatment date +182 days and CM stop date $\geq$ Last Dose of Study Treatment date +182 days Or If CM start Date $>$ Last Dose of Study Treatment date +182 days

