6.8.3. Rescue Medicine

Trade label albuterol/salbutamol metered dose inhalers (MDIs) will be provided as rescue medication throughout the study. Albuterol/salbutamol will be sourced for all centres. Low dose ICS-formoterol as rescue medication is not allowed.

Participants will be dispensed an MDI at Visit 1 to be used primarily to treat asthma symptoms on an as needed basis (see Section 8.4.3). The MDI should be replaced as needed.

Although the use of rescue medications is allowable (at any time during the study), the use of rescue medications should be delayed, if possible, for at least 6 hours prior to the spirometry assessments.

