### 6.2.2.3. Study Treatment Flag for Adverse Events

Study Phase	Definition
Pre-Treatment	AE start date $<$ Study Treatment Start Date
On-Treatment	Study Treatment Start Date $\leq$ AE start date $\leq$ Date of Last Dose + 182 days
Post-Treatment	AE start date $>$ Date of Last Dose + 182 days

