	Missing start day and month	
If study intervention start date is missing (i.e. participant did not start study intervention), then set start date = January 1.
 
Else if study intervention start date is not missing:
 
 
○ If year of start date = year of study intervention start date, then 
 
▪ If stop date contains a full date and stop date is earlier than study intervention start date, then set start date = January 1.
 
▪ Else set start date = study intervention start date.
 
 
 
 
Else set start date = January 1.
		
	Missing end day	A '28/29/30/31' will be used for the day (dependent on the month and year).		
	Missing end day and month	No Imputation		
	Completely missing start/end date	No imputation		
Concomitant Medications/Medical History		
 
• Partial dates for any concomitant medications recorded in the CRF will be imputed using the following convention:
 
 
 
 Missing start day	If study intervention start date is missing (i.e. participant did not start study intervention), then set start date = 1st of month.	
 
	Missing start day	If study intervention start date is missing (i.e. participant did not start study intervention), then set start date = 1st of month.
Missing start day	If study intervention start date is missing (i.e. participant did not start study intervention), then set start date = 1st of month.			

Element	Reporting Detail
	
Else if study intervention start date is not missing:
 
 
○ If month and year of start date = month and year of study intervention start date, then
 
● If stop date contains a full date and stop date is earlier than study intervention start date, then set start date= 1st of month.
 
● Else set start date = study intervention start date.
 
 
Else set start date = 1st of month.

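### The concomitant-medication phase rule never counts a drug started on the first-dose date as on-treatment, and partial-date imputation moves start dates to exactly that day

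*SAP*

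**What the plan says.** SAP 6.2.2.2 has one pre-treatment rule, two on-treatment clauses and two post-treatment clauses for concomitant medication (CM).

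- Pre-treatment: "Concomitant medication (CM) start date $<$ Study Treatment start date".
- On-treatment, first clause: "If CM start date $<$ Study Treatment start date and CM stop date $\geq$ Study Treatment start date".
- On-treatment, second clause: "If Study Treatment start date $<$ CM start Date $<$ Last Dose of Study Treatment date + 182 days".
- Post-treatment, first clause: a start before last dose + 182 days together with "CM stop date $\geq$ Last Dose of Study Treatment date +182 days".
- Post-treatment, second clause: a start after last dose + 182 days.

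The adverse-event rule in SAP 6.2.2.3 is closed at both ends: "Study Treatment Start Date $\leq$ AE start date $\leq$ Date of Last Dose + 182 days". The general rule in SAP 6.2.2.1 also covers every date, but its heading gives way to 6.2.2.2 for medications.

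SAP 6.2.6 allows imputed partial dates to be used for assigning data to phases. For a medication whose start day is missing in the month of first dose, or whose start day and month are missing in the year of first dose, the instruction is "Else set start date = study intervention start date". The one exception is a complete stop date earlier than first dose.

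SAP 6.1.4 lists three medication summaries (asthma, exacerbation and non-asthma). All are limited to medications taken during treatment, which "refers to on treatment period in this study (212895").

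**The concern.** The first-dose date should belong to some phase, and for medications it does not reliably do so. One isolated date might not matter, but 6.2.6 sends uncertain start dates to that very day. The likely purpose of such an imputation is to count an uncertain medication as on-treatment. Combined with 6.2.2.2, it does the opposite.

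Starts genuinely dated to that day are also plausible. Under Protocol 6.8.3, "Participants will be dispensed an MDI at Visit 1 to be used primarily to treat asthma symptoms", and Visit 1 is normally the first-dose visit. Maintenance therapy is reviewed at Visit 1 and may be adjusted.

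At stake is the completeness of the three medication summaries, each of which depends on the on-treatment flag.

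**Working it through.** The plan states no figure on this point, so there is nothing to reproduce. The check is of the rule's logic.

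**Notation.** F = first-dose date; L = last-dose date + 182 days; S and E = medication start and stop. L is at least F + 182 days, so F < L always.

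**Rules in SAP 6.2.2.2.**
- Pre: S < F
- On-1: S < F and E ≥ F
- On-2: F < S < L
- Post-1: S < L and E ≥ L
- Post-2: S > L

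**Start on the first-dose date (S = F).** Pre and On-1 need F < F, which is false. On-2 also needs F < F, which is false. Post-2 needs F > L, which is false. Post-1 holds only if E ≥ L. The record is therefore never on-treatment. It is post-treatment only when E ≥ L, and in no phase otherwise.

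**Start on the upper boundary (S = L).** Pre and On-1 fail because L > F. On-2 and Post-1 need L < L, and Post-2 needs L > L. All fail, so the record has no phase.

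**Boundary cases, before and after closing On-2 to F ≤ S ≤ L.**

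| Start | Stop | As written | On-2 closed |
|---|---|---|---|
| F − 1 day | 5 days after start | Pre, On | Pre, On |
| F | 5 days after start | none | On |
| F | L + 10 days | Post | On, Post |
| F + 1 day | 5 days after start | On | On |
| L | 5 days after start | none | On |
| L + 1 day | 5 days after start | Post | Post |

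**All stop dates for S = F.** Assume the second dose is given 182 days after the first, so L = F + 364. Over stop days 0 to 392 (393 values), days 0 to 363 give no phase (364 values) and days 364 to 392 give post-treatment only (29 values). None gives on-treatment. With a missing stop date, the literal result is no phase. If missing is read as ongoing, it is post-treatment only.

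**Effect of imputation.** Illustrative assumption: first dose on 15 March 2023, second dose 182 days later. Every possible true start in the first-dose month (31 days) or year (365 days) was taken with a fixed course length and a complete stop date. A case counts as truly on-treatment if its true dates qualify under the closed rule. The start was then made partial, imputed under 6.2.6, and classified as 6.2.2.2 is written.

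| Missing part of start | Course length | Truly on-treatment | Flagged on-treatment after imputation |
|---|---|---|---|
| Day, in first-dose month | 10 days | 27 | 0 |
| Day, in first-dose month | 60 days | 31 | 0 |
| Day, in first-dose month | 400 days | 31 | 0 |
| Day and month, in first-dose year | 10 days | 302 | 0 |
| Day and month, in first-dose year | 60 days | 352 | 0 |
| Day and month, in first-dose year | 400 days | 365 | 0 |

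As a check on the third column: a 10-day course reaches 15 March only if it starts on or after 5 March, and 5 to 31 March is 27 days. The zeros do not depend on the example date, because each of these records is imputed to S = F. These are counts of possible dates, not estimates of how often such records occur.

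**The case against.** The strongest reply is that this is a boundary slip in a descriptive derivation, and three larger readings go beyond the documents.

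- **A reader might infer that every such record falls in no phase.** It does not: a recorded stop on or after L makes it post-treatment. What holds without exception is that it is never on-treatment.
- **A reader might infer that nearly every participant is affected, through the rescue inhaler handed out at Visit 1.** Protocol 6.8.3 describes dispensing. It does not say that a medication record is created with that start date. A participant already using the drug would have an earlier start and, with a later recorded stop, would qualify under the first on-treatment clause. SAP 6.1.4 counts participants by ingredient, so one qualifying record keeps a participant in the count even if another is lost. The 637 in Protocol 9.2 is a planning figure for enrolment and says nothing about affected records.
- **A reader might infer that this damages the handling of the intercurrent event of changed maintenance therapy or prohibited medication.** No text ties these tables to that handling, and the strategy wording is redacted. A change started after F and before L is flagged on-treatment anyway.

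Two further points have weight. Not every record imputed to F is truly on-treatment: a drug that ended before first dose but has only a partial stop date is also moved there. And the Output and Programming Specification, which is not available here, may already code the rule differently.

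These limits stand, but the defect remains. The strict signs do not look like a text-extraction fault, since the same table prints ≥ and the adverse-event table prints ≤. The SAP itself does not correct the rule, and a programming specification should not have to contradict it.

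**Conclusion.** The rule is wrong as written and should be corrected. A medication starting on the first-dose date, whether recorded or imputed, cannot reach any of the three during-treatment summaries, whatever its stop date. The upper-boundary gap is real but concerns a single date, and no effect of it has been shown.

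The consequence is limited. Loss is at record level and affects descriptive tables only. No stated primary or secondary estimate uses the medication phase flag. How many records are involved cannot be derived from the documents: it depends on how often start dates are partial and how medications begun at Visit 1 are recorded.

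The conclusion assumes that 6.2.2.2 is programmed literally and that imputed dates are used for phase assignment, as 6.2.6 permits.

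**What to change.** In SAP 6.2.2.2, change only the second on-treatment clause, to: study treatment start date ≤ CM start date ≤ last-dose date + 182 days. This matches the closed bounds of the adverse-event rule in 6.2.2.3.

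Leave the pre-treatment rule, the first on-treatment clause and both post-treatment clauses unchanged. In particular, keep the first post-treatment clause, which captures medications that continue to or past last dose + 182 days. Rewriting post-treatment as only a start after that date would remove a classification the SAP now has.

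With this change every first-dose-date start is on-treatment, and also post-treatment if it continues to L or beyond; a start exactly on L becomes on-treatment. A drug that ended before first dose but has only a partial stop date may then be counted as on-treatment, which is the cautious direction for a table of exposure to other medicines.

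The cost is two inequality signs in the SAP and the matching program line, with a check that the Output and Programming Specification agrees. No new data are needed.

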### 6.2.2.3. Study Treatment Flag for Adverse Events

Study Phase	Definition
Pre-Treatment	AE start date $<$ Study Treatment Start Date
On-Treatment	Study Treatment Start Date $\leq$ AE start date $\leq$ Date of Last Dose + 182 days
Post-Treatment	AE start date $>$ Date of Last Dose + 182 days

#### NOTES:

- If the AE start date is on or after study treatment start date and the study treatment stop date is missing, then the AE will be considered as on-treatment.
- Time of study Treatment dosing and start/stop time of AEs should be considered, if collected.

### 6.2.3. Study Day and Reference Dates

The reference date is the study intervention start date and will be used to calculate study day for efficacy measures and baseline characteristics, as well as efficacy durations. It will also be used to calculate study day for safety measures

The study day is calculated as below:

- Assessment Date = Missing → Study Day = Missing
- Assessment Date < Reference Date → Study Day = Assessment Date – Ref Date
- Assessment Date ≥ Reference Date → Study Day = Assessment Date – Ref Date + 1

#### 6.2.4. Assessment Window

Not applicable for this study.

#### 6.2.5. Multiple measurements at One Analysis Time Point

When triplicate ECG assessments are taken, mean of the measurement will be calculated first and summary statistics will be based on the calculated mean. Triplicate ECG assessment refers to the repeated ECG assessment performed on the same day at the visit. In the case that there are only two repeated ECG assessments performed on the same day, mean of the two measurements will be calculated and used for calculating summary statistics. This will apply to both baseline and post baseline assessments. The individual triplicate ECG assessment will be included in the determination of worst-case on study treatment/post-baseline. The mean of the triplicate assessments will not be used in the determination of worst-case.

For lab tests on a study day, if more than one assessment is taken on the same day, the test from a central lab will be taken over the test from a local lab. If multiple assessments are taken from the same type of lab, the worst case will be used.

#### 6.2.6. Handling of Partial Dates

Element	Reporting Detail					
General	
 
• Partial dates will be displayed as captured in participant listing displays.
 
• However, where necessary, display macros may impute dates as temporary variables for sorting data in listings only. In addition, partial dates may be imputed for ‘slotting’ data to study phases or for specific analysis purposes as outlined below.
 
• Imputed partial dates will not be used to derive study day, time to onset or duration (e.g., time to onset or duration of adverse events), or elapsed time variables (e.g., time since diagnosis). In addition, imputed dates are not used for deriving the last contact date in overall survival analysis dataset.
 
					
Adverse Events	
 
• Partial dates for AE recorded in the CRF will be imputed using the following conventions:           
 
 Missing start day	If study intervention start date is missing (i.e. participant did not start study intervention), then set start date = 1st of month.	
 
 	Else if study intervention start date is not missing:	
 
 
 
		Missing start day	If study intervention start date is missing (i.e. participant did not start study intervention), then set start date = 1st of month.		Else if study intervention start date is not missing:
Missing start day	If study intervention start date is missing (i.e. participant did not start study intervention), then set start date = 1st of month.					
	Else if study intervention start date is not missing:					

Element	Reporting Detail			
		
 
○ If month and year of start date = month and year of study intervention start date, then 
 
▪ If stop date contains a full date and stop date is earlier than study intervention start date, then set start date= 1st of month.
 
▪ Else set start date = study intervention start date.
 
 
 
 
Else set start date = 1st of month.
		
	Missing start day and month	
If study intervention start date is missing (i.e. participant did not start study intervention), then set start date = January 1.
 
Else if study intervention start date is not missing:
 
 
○ If year of start date = year of study intervention start date, then 
 
▪ If stop date contains a full date and stop date is earlier than study intervention start date, then set start date = January 1.
 
▪ Else set start date = study intervention start date.
 
 
 
 
Else set start date = January 1.
		
	Missing end day	A '28/29/30/31' will be used for the day (dependent on the month and year).		
	Missing end day and month	No Imputation		
	Completely missing start/end date	No imputation		
Concomitant Medications/Medical History		
 
• Partial dates for any concomitant medications recorded in the CRF will be imputed using the following convention:
 
 
 
 Missing start day	If study intervention start date is missing (i.e. participant did not start study intervention), then set start date = 1st of month.	
 
	Missing start day	If study intervention start date is missing (i.e. participant did not start study intervention), then set start date = 1st of month.
Missing start day	If study intervention start date is missing (i.e. participant did not start study intervention), then set start date = 1st of month.			

Element	Reporting Detail
	
Else if study intervention start date is not missing:
 
 
○ If month and year of start date = month and year of study intervention start date, then
 
● If stop date contains a full date and stop date is earlier than study intervention start date, then set start date= 1st of month.
 
● Else set start date = study intervention start date.
 
 
Else set start date = 1st of month.

Missing start day and month	
If study intervention start date is missing (i.e. participant did not start study intervention), then set start date = January 1.
 
Else if study intervention start date is not missing:
 
 
○ If year of start date = year of study intervention start date, then 
 
■ If stop date contains a full date and stop date is earlier than study intervention start date, then set start date = January 1.
 
■ Else set start date = study intervention start date.
 
 
 
 
Else set start date = January 1.

Missing end day	A '28/29/30/31' will be used for the day (dependent on the month and year).
Missing end day and month	A '31' will be used for the day and 'Dec' will be used for the month.
Completely missing start/end date	No imputation

